9.1.2 Methods for Assessing and Recording Efficacy Parameters

9.1.2.1 Primary Efficacy Parameter

The number and type of acute serious bacterial infections will be determined through review of data collected on infections. Infections will be reported as AEs which will be obtained by the investigator through observation of the subject (including examinations and investigations), from any information volunteered by the subject, and through active guestioning. Subject diaries will be reviewed to check for instances where the AE occurs and the subject is not on a site visit. Subjects will receive instructions from the investigator on how to record this information in their subject diary (paper) in 'real time' from the time they leave their current site visit until the next site visit, what steps to take if an AE occurs, and the action to be taken if an infection is suspected. If a subject suspects they have an infection between visits, the subject must inform the investigator as soon as possible. If the investigator confirms/suspects the subject has an infection, the subject must attend the site to be examined by the investigator. Subjects will be instructed to bring their subject diary to each study visit. During each scheduled visit, subjects will be asked about AEs occurring since their last visit and subject diaries will be collected and reviewed for any signs of AEs (infections) occurring between visits before IMP administration. Specific diagnostic criteria, as recommended by the FDA guidance (Appendix 3), will be used by the investigator to define each type of serious infection included in the primary efficacy analysis.

Acute serious bacterial infections will include:

- Bacteremia or sepsis
- Bacterial meningitis
- Osteomyelitis/septic arthritis
- Bacterial pneumonia
- Visceral abscess

Essential diagnostic features are defined in the diagnostic criteria for acute serious bacterial infections recommended by the FDA guidance (Appendix 3). The infections must be documented by objective findings. If possible, blood for measurement of acute phase reactants should be obtained, but this is not an absolute requirement. If imaging procedures (i.e., x-rays) are taken to confirm diagnostic criteria for acute serious bacterial infections, data will be recorded in the eCRF.

The investigator will confirm the date of onset of an episode of acute serious bacterial infection and record this in the eCRF.

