Where appropriate, analyses of AEs should take into account the observed intra-subject correlation of the same type or any type of AE, as such within-subject events may not be independent. Methodology for these analyses will be described in the Statistical Analysis Plan (SAP).

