10.5 Primary Efficacy Analysis

The primary efficacy endpoint is the acute serious bacterial infection rate (i.e. the mean number of acute serious bacterial infections per subject-year).

The primary endpoint will be analyzed using the upper 1-sided 99% confidence limit for the acute serious bacterial infection rate, which will be calculated using a Poisson model accounting for the length of the observation period per subject.

A generalized linear model assuming the Poisson distribution for the number of acute serious bacterial infections with the logarithm as link function will be used. The Poisson model will include the natural logarithm of the length of the observation period in years as an offset to account for the (possibly) different lengths of the observation periods per subject.

To assess the primary outcome for efficacy, the null hypothesis of 1 or more acute serious bacterial infections per subject-year will be tested against the 1-sided alternative hypothesis of less than 1 acute serious bacterial infection per subject-year at the 1% level of statistical significance. This 1-sided hypothesis test will utilize the same Poisson model as used for the calculation of the upper confidence limit. Rejection of the null hypothesis if 1 or more acute serious bacterial infection per subject-year will result in the acceptance of the alternate hypothesis of less than 1 acute serious bacterial infection per subject-year.

If sensitivity analyses is to be carried out (the decision will be made during the DRM), this will be performed with the PPS.

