#### 8.1. PRIMARY EFFICACY ENDPOINT AND ANALYSIS

#### 8.1.1. Primary Analysis of Primary Efficacy Endpoint

The primary efficacy endpoint is the rate of acute serious bacterial infections (i.e., the mean number of acute serious bacterial infections per subject-year) and will be based on the total of all of the following events as defined by the FDA: bacteremia or sepsis, bacterial meningitis, osteomyelitis/septic arthritis, bacterial pneumonia, and visceral abscess.

Serious bacterial infections are identified by the following criteria:

- Any AE leading to the following MedDRA PTs: sepsis, bacterial sepsis, bacteremia, meningitis bacterial, osteomyelitis bacterial, arthritis bacterial, pneumonia bacterial, abdominal abscess.

- All AEs leading to any other PT are reviewed by the sponsor for a possible relationship to the primary endpoint (e.g. AEs including one of the following words: bacteremia, sepsis, meningitis, osteomyelitis, arthritis, pneumonia, and abscess). Identified AEs possibly related to the primary endpoint are queried to the investigator to clarify if the AE fulfils the FDA criteria for acute serious bacterial infections. The investigator transfers his decision to the eCRF (AE term).

The date of onset of an episode of acute serious bacterial infections is the day the diagnosis made.

For each subject, the study duration (days) will be calculated as:

(date of last visit) – (date of first infusion) + 1

The number of subject years will be calculated by summing the total subject days and dividing by 365. An estimate of the acute serious bacterial infection rate for BT595 will be obtained by dividing the total number of acute serious bacterial infections by the total number of subject years.

Any intra-subjects correlations of acute serious bacterial infections are not considered to follow a conservative approach for the infection rates.

For the primary efficacy analysis, the acute serious bacterial infection rate for BT595 and the upper 1-sided 99% CI will be estimated by using a Poisson model accounting for the length of the observation period per subject.

A generalized linear model assuming the Poisson distribution for the number of acute serious bacterial infections with the logarithm as link function will be used. The Poisson model will include the natural logarithm of the length of the observation period in years as an offset to account for the (possibly) different lengths of the observation periods per subject.

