To assess the primary outcome for efficacy, the null hypothesis of 1 or more acute serious bacterial infections per subject-year will be tested against the 1-sided alternative hypothesis of less than 1 acute serious bacterial infection per subject-year at the 1% level of statistical significance. This 1-sided hypothesis test will utilize the same Poisson model as used for the calculation of the upper confidence limit. Rejection of the null hypothesis of 1 or more acute serious bacterial infection per subject-year will result in the acceptance of the alternate hypothesis of less than 1 acute serious bacterial infection per subject-year.

The primary efficacy analysis will be tested overall, e.g., without separation by treatment schedule.

Frequency tables presenting the number of subjects with number of experienced serious infections (total and by kind of infection) will be presented.

In addition frequency tables presenting the number of subjects with number of experienced serious infections (total and by kind of infection) for the subgroup of subjects that did not receive treatment for the full period of time, either by missing an infusion or discontinuing the study, will be presented.

A description of each serious bacterial infection will be provided in respective section.

Rate of acute serious bacterial infection will also be compared to relevant historical data from previous PID studies with Intratect® (already marketed 10% IVIg from Biotest) and to available data from Bivigam® (a 10% IVIg, which was formerly developed by Biotest), as well as to available data from the literature. These data will be provided by Biotest by the time of the analyses. The comparison to literature and discussion thereof will be part of the CSR.

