#### 8.1.2. Sensitivity Analysis of Primary Efficacy Endpoint

The same analysis as described in Section 8.1.1 will be performed based on the PPS. The decision regarding this analysis will be made during the DRM.

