Listings will be provided for all AEs, AEs temporally associated with infusion (events beginning during the infusion or up to 72 hours after the completion of the infusion), severe AEs, product related AEs, serious adverse events, serious related adverse events, deaths, AEs resulting in discontinuation, AEs of special interest,. Details regarding severity, product relation, time to onset and stop of AE, information regarding infusion (e.g. infusion number, infusion rate and respective change) and AE outcome will be included as a minimum.

AEs of the same type and of any type shall be presented per subject to elucidate a possible intra subject correlation:

- One table shall enlist AEs by frequency in the following order 1. PT and 2. subject. The number and percentage of the following additional parameters shall be displayed: Seriousness, Severity, Investigator Causality, Infusional AE, Noninfusional AE,
- One table shall enlist AEs by frequency in the following order 1. per subject, 2. per SOC and 3. per PT The number of the following additional parameters shall be displayed: Seriousness, Severity, Investigator Causality, Infusional AE, Noninfusional AE.

The same shall be applied for Infections as defined in 8.2.2

**FDA Specified AE Table**: The AE table as specified below will also be presented.

Adverse reactions (FDA specification) are defined as treatment emergent adverse events, which meet any of the following criteria:

(a) Infusional AE: Adverse events temporally associated with the infusion are adverse events occurring during intravenous administration or within 72 hours after the end of infusion.

(b) Adverse events considered by the investigator to be related to administration of BT595.

(c) Adverse events for which the investigator's causality assessment was missing a worstcase scenario will be applied: The missing relationships will be imputed as 'related'.

The above defined Adverse reactions (FDA Specification), sorted by MedDRA SOC and PT, will be displayed in two columns:

• Number and percent of subjects experiencing the Adverse reaction (FDA Specification) using total number of subject as denominator.
• Number and percent of Adverse reaction (FDA Specification) using total number of infusion as denominator.

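### SAP 8.1.1 calls ignoring within-subject correlation conservative, but if infections cluster in patients the 99% limit is too low and the 1% test too liberal, and no planned analysis corrects this

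*SAP*

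**What the plan says.** SAP 8.1.1 defines the estimate as total infections divided by total subject-years, and then says: "Any intra-subjects correlations of acute serious bacterial infections are not considered to follow a conservative approach for the infection rates". The inference that follows rests on "A generalized linear model assuming the Poisson distribution for the number of acute serious bacterial infections", with a log link and log observation time as offset. No scale parameter, robust variance or negative binomial term is mentioned. The limit and the test share this model: "This 1-sided hypothesis test will utilize the same Poisson model as used for the calculation of the upper confidence limit". Protocol 10.5 agrees; there the limit is "calculated using a Poisson model accounting for the length of the observation period per subject".

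SAP 8.1.2 has the only sensitivity analysis: "The same analysis as described in Section 8.1.1 will be performed based on the PPS". Whether it is run is left to the data review meeting (DRM).

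Elsewhere the documents recognise dependence. Protocol 9.2.3 says of adverse events that "as such within-subject events may not be independent", and Protocol 9.1.2.1 says "Infections will be reported as AEs". SAP 11.3 plans per-subject tables to show intra-subject correlation of adverse events and adds: "The same shall be applied for Infections as defined in 8.2.2". SAP 8.1.1 also plans tables of subjects by number of serious infections and a description of each case.

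**The concern.** A plain Poisson model takes the standard error of the log rate as 1/√x, where x is the total count, however the x infections are spread over patients. If patients differ in underlying risk, or one infection makes another more likely, the variance of the total exceeds its mean. The standard error is then too small, the upper limit too low, and rejection of a rate of 1.0 or more too frequent. That is the opposite of conservative. Without positive clustering the Poisson limit is not too low.

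The trial is uncontrolled and its efficacy claim rests on this one limit. A reader told that the approach is conservative would trust a limit that is too favourable if infections cluster. The planned tables could reveal clustering, but they change neither the limit nor the test. The per-protocol rerun has the same variance assumption.

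**Working it through.** **Inputs.** From SAP 3.5 and 8.1.1: null rate 1.0 per subject-year, planning rate 0.5, one-sided alpha 0.01, 50 evaluable subjects, power at least 80%. Treatment lasts about 12 months, so 50 subjects × 1 year is used. *Assumptions:* the documents give no dispersion and do not say how the limit is computed. Clustering is modelled as gamma frailty with variance k = 0, 0.5, 1 or 2, so variance/mean = 1 + k × rate. The Wald form is the default.

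**1. The plan's own figure.** Wald limit: (x/50) × exp(2.326/√x).
- x = 33: 0.66 × exp(0.405) = 0.9895, success.
- x = 34: 0.68 × exp(0.399) = 1.013, failure.

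The exact limit (0.980 and 1.004) and the score test have the same cut-off of 33. With independent events, P(X ≤ 33) is 0.0070 at mean 50 and 0.950 at mean 25. The power statement therefore holds, with true alpha 0.7%. A likelihood-ratio limit succeeds up to 34 (0.9885; 1.013 at 35).

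**2. Type I error under clustering.** At rate 1.0 the total is negative binomial with size 50/k and success probability 1/(1+k).

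| Variance/mean | Cut-off 33 | Cut-off 34 |
|---|---|---|
| 1 | 0.7% | 1.1% |
| 1.5 | 2.1% | 2.9% |
| 2 | 3.9% | 5.1% |
| 3 | 7.7% | 9.3% |

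With cut-off 33, 1% is passed at variance/mean of about 1.13. Seventy full subject-years do not cure this: 2.3%, 4.1% and 8.0% at 1.5, 2 and 3.

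**3. Same count, different spread.** Subject-level (sandwich) limit: r × exp(t × SE), with r = x/50, t = 2.405 (99% quantile, 49 df) and SE² = Σ(y − r)²/x² × 50/49. With 30 infections the Wald limit is 0.92 in every row.

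| Spread of 30 infections | Σ(y − 0.6)² | SE | Subject-level limit |
|---|---|---|---|
| 30 patients with 1 | 12 | 0.117 | 0.79 |
| 14 with 1, 5 with 2, 2 with 3 | 34 | 0.196 | 0.96 |
| 15 with 2 | 42 | 0.218 | 1.01 |
| 10 with 3 | 72 | 0.286 | 1.19 |

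**4. Counts at which the decision is at risk.** The largest count with a subject-level limit below 1 is 32, 28, 25 and 19 at observed variance/mean 1, 1.5, 2 and 3. With 33 the largest Poisson success, the two disagree at 33, 29–33, 26–33 and 20–33 respectively.

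**5. Low counts.** With 4 infections the Wald limit is 0.26. The subject-level limit is 0.26 (four patients), 0.43 (2 + 2) or 0.89 (all in one patient). No decision changes, but the reported limit does. The chance that the Wald 99% limit falls below the true rate, for k = 0, 0.5, 1 and 2, is 0.7%, 1.2%, 2.0% and 3.7% at rate 0.5. It is under 0.1% at rate 0.2, and 0.7% to 1.0% at rate 0.1 (exact limit used when there are no infections).

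**6. The alternative analysis.** By simulation (200,000 trials per setting), sandwich type I error at rate 1.0 is 0.7%, 1.0%, 1.2% and 1.7% for the same k.

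**The case against.** - **Reading.** The sentence speaks of infection rates and sits next to the point estimate, so it may mean only that recurrent episodes are all counted. That reading is fair, but the sentence also immediately precedes the limit and test, and nothing restricts it.
- **Clustering is hypothetical.** The documents give no dispersion, and Protocol 9.2.3 concerns safety analyses and applies only where appropriate. This stands, and the conclusion is conditional for that reason. The SAP's claim is unconditional and unsupported.
- **Range.** The lower end, 20 infections, needs an observed variance/mean of 3. At the planned 25 infections and a ratio of 2, the subject-level limit is 0.987 and still succeeds, so exactly 25 is at risk only above 2. This stands. Counts vary around 25, however, so disagreement at the planning rate is not rare (figures under the fix).
- **Tables.** The planned tables would make clustering visible. True, but they give no corrected limit or test.
- **Remedy.** If the Poisson result still decides, the type I error is unchanged. Also true: the fix makes the assumption explicit and shows how far the result depends on it. Without clustering, the sandwich limit falls below the Poisson limit in about 40% of simulated trials, so it must not be cited in place of a larger Poisson limit.

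**Conclusion.** The statement is wrong as it stands for the limit and the test, and defensible only for the point estimate. At 50 subject-years, assumed variance/mean of 1.5 to 3 raises the 1% test to between 2.1% and 7.7% (Wald, score or exact cut-off); about 1.13 already exceeds 1%. The decision is vulnerable only at high counts. At true rates of 0.2 or below it hardly changes, and the Wald limit keeps about 99% coverage on average; there, only the reported limit of an individual clustered data set is affected. The size rests on assumed dispersion and one year per subject; the direction needs only positive clustering. This should be fixed, but it does not overturn the design or the power statement.

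**What to change.** In SAP 8.1.1, delete the sentence, or limit it to the point estimate and state that the limit and test assume no clustering. Name the limit used (Wald or likelihood-ratio), because their cut-offs differ by one infection, and say what is reported with no infections, where the Wald limit does not exist.

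In SAP 8.1.2, prespecify one sensitivity analysis on the full analysis set, not subject to the DRM decision: a 99% upper limit and 1% test with subject-level sandwich variance, factor n/(n−1) and the t(n−1) quantile. Report it beside the Poisson limit. State that the Poisson result decides and that the study report will discuss any disagreement.

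State that the subject-level limit is undefined with no infections and unstable with 1 or 2, and add the exact Poisson limit there as a supplement (0.09, 0.13 and 0.17 for 0, 1 and 2 infections in 50 subject-years). With 1 or 2 infections it lies below the Wald limit (0.205 and 0.207), so it must not replace a larger limit.

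The cost is one extra model run and a few sentences; the protocol's primary analysis and power statement do not change. The sponsor accepts a possibly less favourable companion limit. At a true rate of 0.5, the sensitivity analysis would fail where the Poisson test succeeds in about 3%, 10%, 18% and 30% of trials, at variance/mean (at that rate) of 1, 1.25, 1.5 and 2. At a true rate of 0.2 this is 0.3% or less. The sandwich limit holds the error near 1%, not exactly at it.

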#### 8.1.2. Sensitivity Analysis of Primary Efficacy Endpoint

The same analysis as described in Section 8.1.1 will be performed based on the PPS. The decision regarding this analysis will be made during the DRM.

#### 8.2. SECONDARY EFFICACY ENDPOINTS AND ANALYSES

#### 8.2.1. Immunoglobulin G Trough Levels (Total IgG)

Trough levels of total IgG before each infusion will be presented in tabulated statistical summaries of the raw data, absolute and relative changes from baseline values by infusion schedule for all subjects together.

In addition, evaluation of IgG trough levels will include the calculation of the proportion of subjects who failed to meet the target level of  $\geq 5$  g/L at a given visit.

#### 8.2.2. Rate of Any Infections

Infections are identified by the following criteria:

- Any AE leading to the MedDRA SOC "infections and infestation".
- All AEs leading to any other SOC are reviewed by the sponsor for possible relation to an infection (e.g. pyrexia leading to SOC General disorders and administration site conditions). Identified AEs possibly related to this endpoint are queried to the investigator. The investigator transfers his decision to the eCRF (AE term).

The annual rate of infections will be calculated as the mean number of all infections (serious plus nonserious) per subject-year as described in Section 8.1.1. The annual rate per subject will be the total number of infections of the subject divided by the total duration expressed in years of the observation period of the subject. Summaries will be as for a continuous variable and by categorizing the number of any infections per subject according to the following categories:

- 0
- 1
- 2
- 3 to <5
- 5 to <10
- ≥10

The annual rate of days with infections per subject will be the total number of days with infections of the subject divided by the total duration expressed in years of the observation period of the subject.

Frequency tables presenting the number (%) of subjects with infections, the number of days with any infections and the total number of infections will be done.

Tables will also be stratified by season (spring, summer, autumn, winter) using the calendar whereas e.g. spring starts on 01Mar.

In addition, summaries will be done for the subgroup of subjects that did not receive treatment for the full period of time, either by missing an infusion or discontinuing the study.

#### 8.2.3. Rate of Nonserious Infections

The annual rate of nonserious infections will be calculated as the mean number of nonserious infections per subject-year as described in Section 8.1.1. The annual rate per subject will be the total number of nonserious infections of the subject divided by the total duration expressed in years of the observation period of the subject. Summaries will be as for a continuous variable and by categorizing the number of any nonserious infections per subject according to the following categories:

- 0
- 1
- 2

- 3 to < 5
- 5 to <10
- ≥10

The annual rate of days with nonserious infections per subject will be the total number of days with nonserious infections of the subject divided by the total duration expressed in years of the observation period of the subject.

Frequency tables presenting the number (%) of subjects with infections, the number (%) of days with any infections and the total number (%) of infections will be done.

In addition, summaries will be done for the subgroup of subjects that did not receive treatment for the full period of time, either by missing an infusion or discontinuing the study.

#### 8.2.4. Time to Resolution of Infections

Time to resolution of infections (days) will be calculated as infection stop date – infection start date + 1. For the imputation rules of incomplete start/stop dates refer to Section 6.3. The presentation will include the continuous variable and also by categorizing the number of days until the resolution of infection the data according to the following categories:

- 1 to <3
- 3 to <5
- 5 to <8
- 8 to <10
- 10 to <14
- ≥14

Time to resolution will be presented for any infections, serious infections and nonserious infections.

Kaplan-Meier plots will be generated for time to resolution of infection by infusion schedule and overall.

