* "At any dose" does not necessarily imply that the subject is receiving the study drug at the time of the event.

• Diagnosis vs Signs/Symptoms

The investigator should provide a diagnosis rather than individual signs and symptoms, wherever possible and appropriate. However, if there is not enough information to provide a diagnosis, individual signs and symptoms are to be recorded. If a diagnosis is accompanied by unusual symptoms, the diagnosis itself and the unusual symptoms have to be reported separately. For SAEs and other IRAEs, the investigator shall provide any other supporting information that may be required for the assessment of the events, specifically in the free text narrative description of the case. This is of particular importance in situations where a diagnosis cannot (yet) be made. Any subject identifying data on

supporting documents (e.g., name, address, phone number) have to be obliterated prior to sending them to the sponsor.

A complication of an AE constitutes another AE. For example in diarrhea leading to dehydration, diarrhea and dehydration would be captured as separate AEs.

The eCRF provides for a number of items to be completed for each AE. This includes the onset date, end date, intensity/severity, seriousness, action taken with study medication, treatment for the AE, outcome, and causal relationship of the AE with the study medication, other drugs, or study procedures.

• Onset Date, End Date

If an AE started during the study but did not end before the final closing (follow-up) visit, the investigator must make a reasonable effort to establish the outcome and the end date. If this is not possible, e.g., because the AE is still ongoing, or the subject is lost to follow-up, there will be no end date for the AE.

For all AEs that resolve, resolve with sequelae, or have a fatal outcome, an end date must be provided.

If an AE stops and restarts later, all occurrences have to be recorded separately.

If an AE starts as a nonserious AE and becomes serious at a later point in time, the following applies in regard to onset and end dates:

• Intensity/Severity

Refers to the extent to which an AE affects the subject's daily activities. Severity will be categorized according to the following criteria:

	•
Mild	The AE does not interfere with the subject's routine activities.
Moderate	The AE interferes with the subject's daily routine, but usual routine activities can still be carried out.

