Severe	The AE results in inability to perform routine activities.

Table: Adverse Event Severity

Severe vs Serious: The severity is used to describe the intensity of an event. This is not the same as seriousness, which is based on subject/event outcome or action criteria usually associated with events that pose a threat to subject's life or functioning. Seriousness, not severity, serves as the guide for defining regulatory reporting obligations.

Example: While an event may be of "severe" intensity, it may be of relatively minor medical significance, such as severe headache. On the other hand, a myocardial infarction would be usually regarded as serious, even if its intensity is "mild".

Adverse events with changes in severity: If an AE changes in severity, this will be captured as 1 AE, with the highest severity grade recorded.

• Seriousness

For definition of seriousness criteria refer to Section 9.3.1 For an SAE, all seriousness criteria that apply have to be reported. Reporting requirements by the investigator are detailed in Appendix 2.

• Action Taken With Study Medication

The action taken with study medication as a result of the AE has to be documented. In the situation that the AE leads to permanent discontinuation of the study medication, this meets the definition of an AE leading to subject's withdrawal from the study, which is an IRAE. Reporting requirements by the investigator are detailed in Appendix 2.

• Treatment for the Adverse Event

It has to be specified in the eCRF if counteractive treatment was given for the AE. Any treatment for an AE, whether pharmacological or other (e.g., surgical) treatment, has to be recorded in the eCRF.

Outcome

The following categories are used:

Resolved

- Indicates that the event has fully resolved.

- Resolving
 - Indicates that the event is in the process of recovery but has not yet fully resolved.
- Not resolved

- Indicates that the event is ongoing and there has been no recovery.

- Resolved with sequelae
 - Indicates that there is a residual, possibly permanent consequence of the event (e.g., residual hemiparesis subsequent to stroke).
- Fatal
 - Indicates that the subject died due to the event. The outcome "fatal" applies only to the event(s) that were the cause(s) of death. For other AEs that were ongoing at the time of death, the outcome must not be "fatal" but "not resolved".

• Causal Relationship of Adverse Events

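### SAP 8.2.4 puts no condition on AE outcome, so, read literally, an infection that kills the subject is given a time to resolution

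*SAP*

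**What the plan says.** SAP 8.2.4 defines the endpoint by dates alone: "Time to resolution of infections (days) will be calculated as infection stop date – infection start date + 1". The result is summarised as a continuous variable and in six day categories, from 1 to <3 days up to ≥14 days. "Time to resolution will be presented for any infections, serious infections and nonserious infections". A plot is added: "Kaplan-Meier plots will be generated for time to resolution of infection by infusion schedule and overall". Protocol 10.6 uses the same formula. Neither section mentions AE outcome or says what counts as an event or a censored observation in the plot.

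The dates follow rules in Protocol Appendix 1. Under onset and end dates it says: "For all AEs that resolve, resolve with sequelae, or have a fatal outcome, an end date must be provided". An end date is absent only where "the AE is still ongoing, or the subject is lost to follow-up, there will be no end date for the AE".

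The same appendix separates the outcomes. For Resolved: "Indicates that the event has fully resolved". For Fatal: "Indicates that the subject died due to the event". Other events still ongoing at death are to be coded as not resolved.

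SAP 8.2.2 takes as infections all AEs in the infections system organ class, plus others confirmed by query, with no exclusion by outcome. SAP 6.3 imputes an incomplete stop date for any AE that is not ongoing, with no exception for fatal cases. SAP 13.1.5, which records the change to this endpoint, does not mention outcome.

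**The concern.** A stop date means two different things in these data: the infection cleared, or the subject died of it. The formula cannot tell them apart. A fatal sepsis would sit in a table of days until resolution beside infections that were cured.

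The coding is also uneven. If a subject dies of one infection while a second is still active, the second is coded not resolved and has no end date. The infection that caused the death has an end date, so it is the one that receives a resolution time.

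The effect would be most visible in the separate serious-infection summary, where counts are smallest and where sepsis, bacterial meningitis and pneumonia fall. What is at stake is a descriptive table and plot that could mislabel a death. No test depends on it.

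**Working it through.** **Step 1. Follow a fatal infection through the rules.** SAP 8.2.2 selects it as an infection. Protocol Appendix 1 gives it an end date. SAP 8.2.4 subtracts the start date and adds 1. No section of either document removes it, so it has a finite value in the continuous summary and a place in the category table. For the plot the path stops, because no event rule is stated.

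**Step 2. Which category?** The documents do not say that the end date of a fatal AE is the date of death, and they give no time from onset to death. Assuming that it is the date of death, the SAP formula gives:

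| Death, days after onset | Time to resolution (days) | SAP category |
|---|---|---|
| 1 | 2 | 1 to <3 |
| 4 | 5 | 5 to <8 |
| 7 | 8 | 8 to <10 |
| 10 | 11 | 10 to <14 |
| 13 | 14 | ≥14 |
| 30 | 31 | ≥14 |

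A death can land anywhere from the fastest category to the slowest.

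**Step 3. Proportion eventually counted as resolved.** One fatal case among n infections, counted as resolved, adds 1/n. All values of n are assumptions, since the documents give no death rate and no expected count for this summary.

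- n = 5: 1/5 = 20 points
- n = 10: 1/10 = 10 points
- n = 25 (planning rate 0.5 per year × 50 subject-years): 1/25 = 4 points
- n = 35 (0.5 × 70, if all 70 enrolled were followed for a full year): 1/35 = 2.9 points
- n = 250 (an illustrative all-infections count): 1/250 = 0.4 points

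**Step 4. Duration and shape of the curve.** Invented example: ten serious infections, nine resolving at 6, 8, 9, 11, 12, 14, 16, 20 and 25 days (sum 121), one fatal.

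Mean and median:

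- Nine true resolutions only: mean 121/9 = 13.4, median 12.
- Fatal case with a value of 3 days included: mean 124/10 = 12.4, median 11.5.
- Fatal case with a value of 30 days included: mean 151/10 = 15.1, median 13.

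The mean falls in one case and rises in the other.

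Kaplan-Meier readings, fatal case at day 3:

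| Handling of the fatal case | Resolved by day 14 | Resolved in the end |
|---|---|---|
| Counted as an event | 7/10 = 70% | 100% |
| Censored at day 3 | 6/9 = 67% | 9/9 = 100% |
| Kept as never resolved | 6/10 = 60% | 9/10 = 90% |

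Ordinary censoring does not repair the reading. It removes the subject from the risk set as if the infection could still have cleared later.

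**The case against.** Four arguments stand against making much of this.

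**Direction.** A reader might infer that the rule makes fatal infections look like fast resolutions, or that the error always favours the product. The documents do not support either. With an end date 13 or more days after onset, the fatal case falls in the slowest category and can lengthen the mean. The direction is fixed only for the proportion eventually counted as resolved, and the SAP does not list that proportion as an output. It can only be read from the plot, or implied by the category table.

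**Kaplan-Meier plot.** A reader might also infer that the SAP counts death as an event in the plot. It states no event or censoring rule at all. SAP 6.1 places table and figure shells in a separate document that is not part of the text reviewed, and a rule could be there.

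**Source of the data.** Protocol 9.1.2.2 has the subject record time to resolution in the diary and the investigator verify it, and SAP section 8 speaks of diary review. A subject who died would have no resolution to record. This has some force. However, 8.2.4 computes the value from start and stop dates and refers to 6.3 for their imputation, and those are the rules for AE dates. The AE stop date is therefore the likelier source.

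**Visibility.** SAP 8.1.1 promises a description of each serious bacterial infection. SAP 11.3 tabulates events leading to death, lists deaths and includes AE outcome in the listings. A fatal infection would not be hidden. Those displays would still not correct the resolution table.

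**Conclusion.** The gap is real but minor. As written, the formula gives a fatal infection a finite time to resolution in the continuous and categorical summaries, contrary to the protocol's own outcome scale. For the plot, the SAP leaves the event and the censoring undefined.

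The size is conditional on a fatal infection occurring, and the documents do not say how likely that is. If there is one, the proportion eventually counted as resolved rises by 1/n: several points or more in a small serious-infection summary, and negligible across all infections. Mean and median duration may shift up or down, depending on the recorded end date.

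The conclusion rests on the AE stop date being the source of the calculation and on nothing in the unseen shells overriding 8.2.4. The endpoint is secondary, descriptive and untested. A fatal infection that meets the serious bacterial infection criteria still counts in the primary rate, so the primary analysis and the sample size are not touched.

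**What to change.** In SAP 8.2.4:

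- Count an infection as resolved only if the AE outcome is Resolved or Resolved with sequelae.
- Show fatal infections in a separate row of the day-category table and leave them out of the continuous duration summary.
- For the plot, state the event and the censoring. Treat death as a competing event and show the cumulative incidence of resolution, or keep fatal cases unresolved to the end of the time axis. Censor ongoing infections at last contact.

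The cost is a sentence or two in the SAP and one programming condition on the outcome variable, which the eCRF already collects. If no fatal infection occurs, the condition for fatal cases changes no number, and the stated event and censoring rule is still needed to produce the plot.
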